## **6. Data Collection and Management**

### **6.1 Case Report Form / Electronic Data Recording**

#### **6.1.1 Case Report Form Design**

This study will use an electronic Case Report Form (eCRF) specifically designed according to the study protocol. The eCRF will clearly define all data items to be collected, including but not limited to patient demographics, medical history, diagnostic information, laboratory results, imaging assessments, pathology reports, treatment regimens, and outcome measures.

#### **6.1.2 Data Sources and Recording**

All study data will be obtained from the authorized medical information systems of each participating center, primarily including the Hospital Information System (HIS), Laboratory Information System (LIS), Pathology Information System (PIS), and Picture Archiving and Communication System (PACS). Data recorders will extract information directly from these source systems and accurately and completely enter it into the corresponding fields of the eCRF.

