**(9) Overall Survival (OS)**

The time interval (in months) from the date of initial surgery to the date of death from any cause. Surviving patients are censored at the date of last follow-up.

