**(10) Overall Survival Rate**

The cumulative probability of survival at 1, 3, 5, and 10 years after surgery, estimated by the Kaplan-Meier method.

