##### **(1) Descriptive analysis**

- **Demographic and clinicopathological characteristics:** Continuous variables will first be tested for normality (Shapiro-Wilk test). Normally distributed variables will be presented as mean  $\pm$  SD, with group comparisons using t-test or ANOVA; non-normally distributed variables as median (IQR), with group comparisons using Mann-Whitney U or Kruskal-Wallis test. Categorical variables as frequency (%), with group comparisons using Pearson  $\chi^2$  test or Fisher's exact test (when expected frequency  $<5$ ).
- **Treatment patterns:** Distributions and temporal trends (e.g., by 5-year intervals) of surgical procedures, margin status, lymph node surgery, and adjuvant radiotherapy/chemotherapy will be described, stratified by pathological grade and time period.
- **Outcome events:** Local recurrence rate, distant metastasis rate, and tumor-specific mortality rate will be calculated for the overall cohort and by pathological grade. Time to recurrence, number of recurrences, and proportion/probability of grade progression after recurrence will be described.

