### **(5) Bias control (as described in 5.3) – PSM, IPTW, E-value.**

### **(6) Stratified, subgroup, and sensitivity analyses**

- **Stratified analysis:** All primary analyses will be stratified by pathological grade (benign/borderline/malignant) to compare prognostic factors across grades.
- **Pre-specified subgroups:** Age (<35 vs. ≥35 years), tumor size (<5 cm vs. ≥5 cm), surgical procedure (segmental resection vs. minimally invasive rotary

excision, wide local excision vs. total mastectomy). Forest plots will display subgroup HRs with interaction P-values.

- **Sensitivity analyses:**
  - Complete case analysis vs. multiple imputation.
  - Varying PSM parameters (1:1 vs. 1:2 matching, caliper 0.1 vs. 0.2).
  - Separate analysis of recurrence definitions (ipsilateral chest wall/axilla only) to exclude misclassification.
  - Excluding patients with follow-up <6 months.
  - For OS, competing risk analysis with death from PT vs. other causes.

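### The plan gives no source for deaths outside the centres' own systems, no cause-of-death rule and no last-known-alive date, so OS and tumor-specific mortality may rest on incomplete deaths, with bias of unknown size and direction

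*Combined protocol and SAP*

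**What the plan says.** **Data source.** Section 6.1.2: "All study data will be obtained from the authorized medical information systems of each participating center". It names mainly the hospital, laboratory, pathology and imaging systems, and adds: "Data recorders will extract information directly from these source systems". Where a follow-up outcome is missing, Section 6.2.3 sends staff back to the medical records.

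**What deaths are needed for.** OS is a primary endpoint, defined in Section 3.2.1(9) as "The time interval (in months) from the date of initial surgery to the date of death from any cause". The censoring rule is "Surviving patients are censored at the date of last follow-up". Section 3.2.1(10) asks for "The cumulative probability of survival at 1, 3, 5, and 10 years after surgery, estimated by the Kaplan-Meier method". Section 5.4.2(1) adds "Local recurrence rate, distant metastasis rate, and tumor-specific mortality rate will be calculated for the overall cohort and by pathological grade". Section 5.4.2(6) lists "For OS, competing risk analysis with death from PT vs. other causes". Section 5.4.2(2) treats death as the competing event for local recurrence and distant metastasis.

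**Loss to follow-up.** Section 4.2(3) excludes patients who are lost to follow-up or whose follow-up outcomes are missing. It gives no threshold and no expected rate.

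**The concern.** Section 6.1.2 restricts where data may come from. Followed as written, no step would find a death that a centre's own systems do not hold. A woman whose death elsewhere is never reported to the centre is either censored at an undefined last follow-up date or dropped from the cohort. In both cases her death is not counted.

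The quality controls do not reach this. Double extraction of death (Section 5.3(2)) and 10% source verification (Section 6.2.3) compare the eCRF with hospital records, so they cannot detect a death missing from those records. E-values address confounding. None of the sensitivity analyses in Section 5.4.2(6) varies death ascertainment. The follow-up table in Section 6.2.4 is a place to store the data; how it is filled is not described.

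At stake are the 5- and 10-year OS estimates, the split of deaths by cause, the competing-risk results for recurrence and metastasis, and the comparisons across grades if ascertainment differs by grade.

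**Working it through.** **1. The plan's own figure.** Section 5.4.1 gives one expected event count, about 380 local recurrences. It reproduces: 3,500 × 0.11 = 385. With the stated 7:2:1 grade mix and the recurrence rates in Section 2.2.2, 0.7 × 7.1% + 0.2 × 16.7% + 0.1 × 25.1% = 10.82%, or 379 events. No count or rate is given for death, so nothing in the plan sizes this point. Every survival, capture and loss value below is an assumption.

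**2. Missed deaths kept at risk.** Let S be true 10-year OS and c the share of deaths captured.
- Model A, missed deaths counted alive to the cut-off: observed OS = 1 − c(1 − S).
- Model B, missed deaths censored at about the time of death: observed OS = S^c.

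| True S | c = 70% (A / B) | c = 50% (A / B) | c = 30% (A / B) |
|---|---|---|---|
| 97% | 97.9 / 97.9 | 98.5 / 98.5 | 99.1 / 99.1 |
| 90% | 93.0 / 92.9 | 95.0 / 94.9 | 97.0 / 96.9 |
| 80% | 86.0 / 85.5 | 90.0 / 89.4 | 94.0 / 93.5 |
| 70% | 79.0 / 77.9 | 85.0 / 83.7 | 91.0 / 89.9 |

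OS is overstated by 1 to 2 points when deaths are few (S = 97%) and by up to 21 points when they are common (S = 70%, c = 30%, model A).

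**3. Drop-out unrelated to death.** If patients stop attending for reasons independent of death and are censored at the last visit, this is ordinary right censoring. In a simulation of 2,000,000 patients with constant hazard and independent drop-out, the drop-out rate was set so that 30%, 50% or 70% of 10-year deaths were recorded. The Kaplan-Meier estimate was 89.9% to 90.0% for a true 90%, and 80.0% to 80.1% for a true 80%. A low capture share alone therefore produces no bias.

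**4. Exclusion under Section 4.2(3).** Let a share e of survivors be excluded as lost, and let uncaptured deaths be excluded too. Observed OS = S(1 − e) / [S(1 − e) + (1 − S)c]. With S = 90%:
- c = 50%, e = 0: 0.90 / (0.90 + 0.05) = 94.7%, overstated.
- c = 50%, e = 50%: 0.45 / (0.45 + 0.05) = 90.0%, no bias.
- c = 70%, e = 50%: 0.45 / (0.45 + 0.07) = 86.5%, understated.

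The sign depends on whether survivors are retained more often (1 − e > c) or less often (1 − e < c) than deaths are captured. The plan fixes neither quantity.

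**The case against.** The strongest reply is that the documents nowhere say the centres' systems lack outside deaths. The list of systems in Section 6.1.2 is open-ended, death is a named extracted outcome, Section 6.2.4 plans a follow-up table, and Section 4.1(3) requires follow-up data for entry. Telephone or family contacts may already be stored in those systems. This stands in part: a reader might infer that OS cannot be measured at all, and the text does not support that. Some deaths will be captured; what cannot be shown is how completely.

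A reader might also conclude that survival is certainly overstated. That does not follow either. Overstatement needs loss of contact to be related to death, or survivors to be dated alive beyond their last real contact. Steps 3 and 4 show no bias, or the opposite bias, under other conditions the plan equally allows.

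A third tempting step is to divide assumed capture shares in malignant and benign disease and read the ratio as inflation of the grade hazard ratio. It relies on the same at-risk assumption as step 2. Deaths long after a benign excision and an unrelated end of attendance are close to the case where last-visit censoring does no harm.

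Finally, nothing shows that the centres can query a death registry, and linkage would need ethics approval under Section 7. That limits one possible remedy; it does not close the gap.

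**Conclusion.** The concern holds as an ascertainment gap. All-cause OS to 10 years, tumor-specific mortality and the analyses with death as competing event may rest on incomplete deaths, because the plan gives no source for deaths outside the centres' systems, no cause-of-death rule and no last-known-alive date. OS is probably overstated if loss of contact is related to death or if survivors are dated alive past their last contact. It can be understated if patients who stop attending are excluded under Section 4.2(3). Size and direction are unknown.

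The range of 92.9% to 96.9% for a true 90% is a worst-case illustration. It rests on assumed capture of 70% to 30% and on missed deaths staying at risk until about the time of death. No stated sample-size figure changes. This is a cheap improvement that alters what the study may claim about survival. If active follow-up already feeds these systems, the sponsor can answer much of the point by stating that source together with the two missing rules.

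**What to change.** 1. **Section 3.2.1(9):** define the OS censoring date as the last date the patient is documented alive. For OS, do not apply the loss-to-follow-up exclusion in Section 4.2(3); censor those patients at that date.
2. **Reporting:** give the share of patients with known vital status at 5 and 10 years, by grade and centre.
3. **Section 5.4.2(6):** add a bounding sensitivity analysis that varies death ascertainment by grade among patients of unknown status.
4. **Labelling:** state how cause of death is assigned. Where vital status is not confirmed from outside the hospital systems, describe OS and tumor-specific mortality as based on hospital-recorded deaths.
5. **Where possible:** if a centre already has access to a death-registration source and ethics approval is obtained (Section 7), query it before identifiers are stripped (Section 6.2.1). Do not count non-matches as alive unless the source's coverage is known.

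Cost: items 1 to 4 need a text revision, some extra analysis and a less favourable label on the survival results, but no new data source. Item 5 needs an ethics amendment and work at the centres.

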#### **6.1.3 Electronic Data Recording System**

The electronic data capture system used in this study will have comprehensive functions including user permission management, data audit trails, and electronic signatures, ensuring the standardization and traceability of the data entry process. All modifications to entered data will be automatically recorded by the system, including the modifier,

modification time, and reason for modification.

## **6.2 Data Management**

### **6.2.1 Data Anonymization**

All extracted data will be stripped of direct identifiers such as name and ID number, and will only be identified by a study number. Data access will be restricted to the principal investigator and designated data analysts.

### **6.2.2 Data Storage**

Data will be stored electronically. All final confirmed study data will be stored on a securely encrypted server managed by the hospital information center, within a research-dedicated database.

### **6.2.3 Data Integrity Checks**

- **Source Data Verification (SDV):** The project team will randomly select 10% of cases. A quality control officer will compare the data in the eCRF with the original hospital electronic medical records item by item to ensure transcription accuracy.
- **Logical Checks:** Logic validation rules will be embedded at the database design stage (e.g., surgery date cannot be later than recurrence date; tumor size cannot be negative). The system will automatically flag data points that violate logic, requiring mandatory review.
- **Missing Value Management:** The system will generate regular missing value reports. For critical variables (e.g., pathological grade, surgical margin status, follow-up outcomes), every effort will be made to trace back to medical records for supplementation. If supplementation is truly impossible, the value will be clearly recorded as "missing" and its impact will be assessed in subsequent statistical analyses.

### **6.2.4 Database Establishment and Management Methods**

The database will contain multiple interrelated tables, such as: patient basic information table, diagnosis information table, surgical treatment table, pathological characteristics table, follow-up information table, and molecular biomarker results table. All tables will be linked through a unique medical record number.

- **Variable Definition:** A detailed Data Dictionary will be developed to clearly define each variable in the eCRF (including variable name, type, value meaning, unit, source of collection, etc.), ensuring consistent understanding among all research personnel.
- **Blinding:** Data entry personnel will be blinded to patients' final follow-up outcomes (whether recurrence/metastasis occurred) during the entry of clinical and pathological data, to avoid introducing subjective bias at the data entry stage.
- **Quality Monitoring:** Regular centralized monitoring of data quality will be performed, with reports on outliers, logical errors, data consistency, and data entry progress.
- **Database Lock:** After final data cleaning, verification, and confirmation, the database will be formally locked, and any unauthorized modifications will be prohibited. Any request to modify locked data must be approved by the principal investigator, with detailed documentation of the reason, content, and date of modification, and the locking process will need to be repeated. The data lock for this study is planned to occur once, just before the formal statistical analysis begins.

## 7. Ethical Requirements

This study will be conducted in compliance with the Good Clinical Practice (GCP) for Drug Clinical Trials, the Measures for the Administration of Investigator-Initiated Clinical Research in Medical and Health Institutions (for trial implementation), and the Declaration of Helsinki. The study will not begin until the protocol has been approved by the Ethics Committee of our hospital. During the research process, if protocol amendments are necessary, the revised protocol must be resubmitted to the Ethics Committee for review, and the investigator must wait for the Ethics Committee's approval before implementing the new protocol.

This study will collect clinical data and personal information from research subjects for scientific research purposes, which involves patients' privacy rights. All study personnel and data analysts will sign confidentiality agreements and will not disclose

patients' personal information or disease-related information to any individuals or institutions unrelated to this study. All collected patient data will be uniformly managed to prevent any leakage of personal privacy.

